9.4 Description of Statistical Methods

9.4.1 General Approach

This is a single arm study (i.e., no sham, placebo or alternative treatment included). The primary objective (clinical success rate) will be assessed as a binary outcome of whether or not each patient shows clinical success as defined above. The response rate will be summarized in terms of the observed proportion of patients manifesting a positive response and a two-sided exact 95% confidence interval (CI) per the Blyth-Still-Casella method. KOOS pain scores and pain VAS will be assessed as mean and standard deviation.

9.4.2 Analysis of the Primary Efficacy Endpoint(s)

The primary endpoint is the clinical success rate at 6-month follow-up compared to baseline as a binary assessment.

9.4.3 Analysis of the Secondary Endpoint(s)

Analysis of secondary endpoints include: (1) changes in the mean KOOS and VAS pain scores, the mean (2) the technical success rate (defined as the proportion of patients for whom the procedure was successfully completed); (3) the adverse event rate (defined as the proportion of patients showing each type of adverse event or any adverse event); (4) reduction in the usage of pain medication and the need for physical therapy. A point estimate and 95% confidence interval will be provided for each secondary outcome at each time and for the change in each outcome from baseline to each post-treatment follow-up visit. Changes in the outcomes from baseline to follow-up will be tested using the paired-sample Wilcoxon signed rank test for the KOOS and VAS scores and the McNemar test for the other measures which will be assessed as binary outcomes (e.g., whether or not the patient reported usage of pain medication on a daily basis).

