Methodology	Prospective, single-arm (no sham or placebo), single-center
Endpoint	
Primary Efficacy endpoint: KOOS pain score at 6-months post intervention
 
Secondary endpoints:
 
 - Rate, type, causality, and severity of adverse events (AEs) - KOOS scores at 3-, 6-, 12-, and 24-month visits - QOL index value at 3-, 6-, 12-, and 24-month visits - Pain visual analog scale (VAS) at 3-, 6-, 12-, and 24-month visits - Magnetic Resonance Angiogram (MRA) findings at 6 and 24-month visits
Study Duration	4 years
Participant Duration	Each individual subject will be enrolled for approximately 25 months to complete all study visits from the initial screening visit to last follow up at 24-months post intervention
Population	40 patients, age 30-85, of any gender, with knee pain resistant to conservative management for at least 9 months post TKA.
Study Sites	NYU Langone Health Hospitals
Number of participants	Data from 40 patients who complete 6-month visit will be required The study would enroll 50 patients to account for an attrition rate of 20%
Description of Study Agent/Procedure	Embozene™ Color-Advanced Microspheres are spherical, tightly calibrated, biocompatible, non-resorbable, hydrogel microspheres coated with an inorganic perfluorinated polymer used for embolization.
Key Procedures	GAE; a transcatheter arterial embolization of one or more genicular artery(ies) using Embozene™ Color-Advanced Microspheres

Statistical Analysis	
The primary objective is to assess the clinical success rate, which will be summarized in terms of the observed proportion of patients manifesting a positive response and a two-sided exact 95% confidence interval (CI) per the Blyth-Still-Casella method. The treatment will be declared a success if the data support the conclusion that at least 75% of treated patients show a positive response.
 
Preliminary analysis will be performed after 25% (10 subjects) of study sample size complete the 6-month follow-up visit.

----------------------	---

Schematic of Study Design

1 Introduction, Background Information and Scientific Rationale

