3.2.2 Secondary Study Endpoints

Secondary efficacy endpoints are:

1. KOOS scores at 3-, 6-, 12-, and 24-month post GAE
2. VAS pain at 3-, 6-, 12-, and 24-month post GAE
3. Self-reported quality of life using EQ-5D-5L scale at 3-, 6-, 12-, and 24-month post GAE
4. MRA findings at 6- and 24-month post GAE
5. Pain medication usage at 3-, 6-, 12-, and 24-month post GAE
6. Feasibility / technical success
7. Knee-specific biomarkers at 3-, 6-, 12-, and 24-month post GAE
8. Number/rate, severity, and description of complications, adverse events, or poor outcomes that are secondary to the procedure, which will be summarized using counts and simple statistics (i.e., mean number of patients with complications.)

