4.6 Total Number of Participants and Sites

Data from 40 participant will be required and the study would accrue 50 patients to account for an attrition rate of 20%. Withdrawn subjects and subjects who did not completed at least the 6-month visit can be replaced.

The study will be conducted only at NYULH Hospitals. No subjects will be enrolled at external national or international sites.

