9.3 Analysis Datasets

Participants who received study device and complete at least one follow-up visit (3-month visit) will be included in the study analysis.

Preliminary analysis will be performed after 25% (10 subjects) of study sample size complete the 6-month follow-up visit.

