9.5 Sample Size

The sample size is selected based on primary objective so that the study will have 80% power at the 5% significance level for testing the null hypothesis $H_0: PT \leq 0.5$ against the alternative hypothesis $H_A: PT \geq 0.75$, where PT is the true proportion of patients that will manifest a positive treatment response. As a result, the study should have 40 patients who completed the 6 months visit since this sample size will endow the test with 80.4% power at a realized significance level of 0.047 with 20% attrition, the study will need 50 subjects to reach the target sample size.

With 20% with 20% attrition, the study will need to enroll 50 patients. The PI and sub-investigators determined that increase in the sample size is necessary to evaluate the role of GAE as a disease-modifying treatment option for knee OA. Since this current study is the only active study in the U.S collecting samples for biomarker analysis and the need for a larger sample size to evaluate changes in biomarker levels, an increase in sample size is needed.

10 Source Documents and Access to Source Data/Documents

Source data is all information, original records of clinical findings, observations, or other activities in a clinical trial necessary for the reconstruction and evaluation of the trial. Source data are contained in source documents.

Examples of these original documents, and data records include: hospital records, clinical and office charts, laboratory notes, memoranda, subjects' diaries or evaluation checklists, pharmacy dispensing records, recorded data from automated instruments, copies or transcriptions certified after verification as being accurate and complete, microfiches, photographic negatives, microfilm or magnetic media, x-rays or other imaging studies, subject files, and records kept at the pharmacy, at the laboratories, and at medico-technical departments involved in the clinical trial. It is acceptable to use paper CRFs as source documents. Source CRFs can also be documented in the electronic medical record (EPIC).

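### KOOS and VAS change is estimated and tested visit by visit on patients with both values, with no method for missed visits, so results to 24 months are biased if loss depends on outcome

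*Combined protocol and SAP*

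**What the plan says.** - **Test and estimates (9.4.3).** "Changes in the outcomes from baseline to follow-up will be tested using the paired-sample Wilcoxon signed rank test for the KOOS and VAS scores". The same section promises a point estimate and 95% CI at each time and "for the change in each outcome from baseline to each post-treatment follow-up visit". Section 9.4.1 adds that "KOOS pain scores and pain VAS will be assessed as mean and standard deviation".
- **Visits (3.2.2).** The endpoints include "KOOS scores at 3-, 6-, 12-, and 24-month post GAE", and VAS pain has the same four visits. Section 2.2 makes improvement at those visits a secondary objective.
- **Analysis set (9.3).** "Participants who received study device and complete at least one follow-up visit (3-month visit) will be included in the study analysis". No 6-, 12- or 24-month visit is required, and no rule covers a later visit that is missed.
- **Expected loss (9.5).** "with 20% attrition, the study will need 50 subjects to reach the target sample size". The target is 40 patients with a 6-month visit. No figure is given for 12 or 24 months.
- **Replacement (4.6).** "Withdrawn subjects and subjects who did not completed at least the 6-month visit can be replaced".
- **Data after withdrawal.** Section 4.7.2 asks staff to try to complete the follow-up assessments, and the early-termination visit (6.3.5) includes the questionnaires. Neither says how those data enter the analysis.
- **No later document.** Section 9.1 says that there will be no formal SAP. No imputation, longitudinal model, missing-data assumption or sensitivity analysis is stated anywhere.

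**The concern.** A paired analysis at a given visit needs a baseline value and a value at that visit. With no rule for missed visits, the 6-, 12- and 24-month results come only from patients who attended then. A patient with a poor 3-month score who is then lost belongs to the analysis set but does not contribute to the later visits, and the 3-month score is not used to inform them.

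If the patients who leave differ in outcome from those who stay, the mean change among those who stay drifts from visit to visit even when the true effect is constant. In a single-arm study no comparison group would show this. At stake is the claim about durability to 24 months: a constant or fading effect could look like a growing one, or the reverse. Replacement restores the number of patients but not the outcomes of those who left. The 3-month result is also exposed, because section 9.3 drops treated patients without that visit.

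**Working it through.** **1. The plan's own figure.** 40 / (1 − 0.20) = 50, so the attrition allowance reproduces. It is tied to the 6-month visit. The documents give no SD of change, no between-visit correlation and no later attrition, so all of these are assumptions below.

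**2. Upper bound at one visit.** Suppose changes are normal and the worst fraction d is missing. The mean improvement is then overstated by SD × φ(z_d) / (1 − d). For d = 0.20, z = −0.842 and φ = 0.280, which gives 0.280 / 0.80 = 0.35 SD.

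| Missing (worst fraction) | Overstatement, SD of change | At SD 27 mm |
|---|---|---|
| 10% | 0.19 | 5.3 mm |
| 20% | 0.35 | 9.4 mm |
| 30% | 0.50 | 13.4 mm |
| 40% | 0.64 | 17.4 mm |

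The 27 mm is the 6-month VAS SD of the 20-patient native-knee study described in section 1.2.2. It is borrowed here as an SD of change.

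**3. Less extreme selective loss, four visits.** Assumptions: 50 patients, true change 15 at every visit, SD of change 20, correlation 0.7 between visits, everyone seen at 3 months. The loss rate per interval depends on whether the change is below 15.

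Hand check at 6 months, with 32% loss below 15 and 6% otherwise:
- Half the patients lie below 15, so the share missing is 0.5 × 0.32 + 0.5 × 0.06 = 19%.
- Each half lies on average 0.798 × 20 = 15.96 points from the mean.
- Among those who stay, the 3-month mean is too high by 15.96 × (0.94 − 0.68) / (0.94 + 0.68) = 2.56.
- Carried to 6 months: 0.7 × 2.56 = 1.8, so 15 appears as about 16.8. Simulation gives 16.7.

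Continuing the same rule, complete pairs show 16.7, 18.5 and 20.2 at 6, 12 and 24 months with 19%, 34% and 45% missing. At 24 months, under different loss rules:

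| Loss per interval (below 15 / otherwise) | Missing at 24 months | Complete pairs | Likelihood-based model |
|---|---|---|---|
| 32% / 6%, on last observed score | 45% | 20.2 | 15.0 |
| 14% / 3%, on last observed score | 23% | 17.0 | about 15 |
| 12% / 6%, on last observed score | 24% | 16.2 | about 15 |
| Equal rates | – | about 15 | about 15 |
| 6% / 32% (patients doing well leave) | 45% | 9.7 | about 15 |
| 32% / 6%, on the unseen current score | about 45% | 21.0 | 16.9 |

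The 14% / 3% row implies 0.5 × 0.14 + 0.5 × 0.03 = 8.5% missing at 6 months, which is below the plan's 20%.

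**4. Effect on the test.** Assumptions: no true change, 50 patients, SD 27 mm, correlation 0.6 between 3 months and the later visit, two-sided 5% Wilcoxon test (2.5% nominal for benefit).

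| Who is missing (20%) | Complete-pair mean | Significant benefit | Estimate using all 3-month scores |
|---|---|---|---|
| Unrelated to outcome | +0.1 mm | 2.3% | about 0 |
| Partly those with poor 3-month scores | +3.9 mm | 16% | about 0 |
| Worst at the visit itself | +9.2 mm | 64% | +6.9 mm |
| Partly those with good 3-month scores | −3.9 mm | 0.3% | about 0 |

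With 40% missing, the second row rises to 30% significant benefit.

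**The case against.** Several counter-arguments stand and limit the point.

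- **The Wilcoxon test is not the cause.** A reader might infer from section 9.4.3 that it is. A paired t-test, and the planned mean changes and intervals, would carry the same bias. The source is the restriction to complete pairs, a phrase that the protocol does not use but which follows from a paired analysis without a missing-visit rule. Reporting mean change beside a signed-rank test is common in a small pilot and is not itself an error.
- **The direction is not known.** A reader might infer that benefit will be overstated. Nothing in the documents says who will leave, and the bias vanishes or reverses under other patterns.
- **Patients who withdraw may still supply data.** Sections 4.7.2 and 6.3.5 seek questionnaires from them, so it is not established that they add nothing later. What is missing is a rule for using those data.
- **A mixed model is not a cure.** Its recovery of 15 holds when observed scores explain the loss. When loss depends on the unseen score, bias remains, although less of it (16.9 against 21.0).
- **These are secondary endpoints in a pilot.** Section 9.2 declares success on the binary 6-month rate, which this point does not touch.

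None of this supplies the missing method. The plan expects loss, follows patients for 24 months and commits to estimates and tests at every visit.

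**Conclusion.** The concern holds in conditional form. As written, sections 9.3 and 9.4.3 give KOOS and VAS changes, intervals and tests that are valid only if loss is unrelated to outcome. With SD 20 and correlation 0.7, selective loss of poor responders turns a true 24-month change of 15 into about 17 (23% missing) or about 20 (45% missing). At 6 months, the only visit with a planned attrition figure, the heavier scenario adds 1.7 points. These sizes rest on assumed SD, correlation and loss rates and should be read as a range. They do not show that benefit will be overstated in this trial. A likelihood-based analysis of all visits does better in every selective-loss pattern examined and no worse when loss is unrelated to outcome. The change is worth making before database lock, but the primary success rule does not depend on it.

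**What to change.** - **9.4.3, main analysis.** For each KOOS subscale and VAS, fit one mixed model for repeated measures with baseline and all follow-up visits as responses and visit as a factor. Report mean change and 95% CI per visit from the model. Use an unstructured covariance: with five time points this has 5 × 6 / 2 = 15 parameters on about 50 patients, so name a simpler fallback structure in advance and apply a small-sample degrees-of-freedom correction.
- **9.3.** State that for this analysis all treated patients with a baseline are included, whether or not they attended at 3 months.
- **Post-withdrawal data.** State that questionnaires obtained after withdrawal or at the early-termination visit are used at the matching visit.
- **Sensitivity analysis.** Add a simple one for loss related to unseen outcomes, for example a delta shift applied to missing visits. Tabulate missing visits with reasons.
- **Wilcoxon test.** Keep it as a supportive check on the normality assumption only. It cannot check missing-at-random, because on complete pairs it needs a stronger assumption about loss.

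The cost is a few sentences in two sections and a little programming, with no new data. The downside is reliance on missing-at-random and approximate normality in the main analysis.

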9.4.4 Safety Analyses

Safety endpoints will assess adverse event rate (defined as the proportion of patients showing each type of adverse event or any adverse event). The severity and causality of all adverse events will be graded according to the new adverse event classification by the Society of Interventional Radiology Standards of Practice Committee.

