DSMB	Data and Safety Monitoring Board
FFR	Federal Financial Report
FWA	Federalwide Assurance
GAE	Genicular Artery Embolization
GCP	Good Clinical Practice
HIPAA	Health Insurance Portability and Accountability Act
ICF	Informed Consent Form
ICH	International Conference on Harmonisation
IRB	Institutional Review Board
ISM	Independent Safety Monitor
KOOS	Knee Injury and Osteoarthritis Outcome Score
MRA	Magnetic Resonance Angiogram
MOP	Manual of Procedures
N	Number (typically refers to participants)
NIH	National Institutes of Health
OA	Osteoarthritis
OHRP	Office for Human Research Protections
OHSR	Office of Human Subjects Research
PI	Principal Investigator
QA	Quality Assurance
QC	Quality Control
QOL	Quality of Life
SAE	Serious Adverse Event/Serious Adverse Experience
SOP	Standard Operating Procedure
TKA	Total Knee Arthroplasty
US	United States
VAS	Visual Analogue Scale

Protocol Summary

Title	Prospective pilot study on geniculate artery embolization for treatment of persistent knee pain post total knee arthroplasty
Short Title	Geniculate artery embolization for post TKA pain
Brief Summary	Single-arm, single-center, no sham or placebo, prospective pilot trial designed to evaluate the safety and efficacy of transcatheter arterial embolization in patients with persistent knee pain resistant to conservative management for at least 9 months after total knee arthroplasty (TKA). Eligible participants will receive geniculate artery embolization (GAE) using Embozene™ Color-Advanced Microspheres. Patients will be followed up for a total of 24 months after GAE.
Phase	Pilot study
Objectives	
Primary objective: to determine the effectiveness of GAE in reducing knee pain at 6-months post GAE in patients with persistent knee pain after TKA. This will be assessed by evaluating the clinical success rate defined as at least 15% improvement in Knee injury and Osteoarthritis Outcome Score (KOOS) pain score from baseline to follow-up visit at 6 months post-intervention without an increase in baseline incidence of pain medication use or intra-articular injections.
 
Secondary objectives:
 
 - To evaluate the safety of GAE - To determine feasibility and technical success of GAE - To determine whether GAE improves knee symptoms and quality of life (QOL) - To determine the effect of GAE on disease-specific biomarkers in the blood, urine, and synovial fluid of the target knee

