2.2 Secondary Objectives

The secondary objectives of the study are to determine

1. Safety of GAE evaluated by cumulative rates of adverse events (AE), as well as type, causality, and severity of each AE.
2. Feasibility / technical success defined as successful selective catheterization of target genicular artery(ies) and embolization from at least one feeding artery of the knee joint (with the embolization endpoint defined as suppression or reduction in the filling of (blood flow in) abnormal vessels visible on angiography (pruning of the distal abnormal vasculature, with patent genicular artery)).
3. Whether GAE is effective in improving:
 - a. Knee pain using the visual analog scale (VAS) at 3-, 6-, 12-, and 24-month post GAE
 - b. Knee symptoms using KOOS scores at 3-, 6-, 12-, and 24-month post GAE [60]
 - c. Self-reported quality of life using EQ-5D-5L scale at 3-, 6-, 12-, and 24-month post GAE [61].
 - d. Synovitis on MRA at 6- and 24- months post intervention
4. Effect of GAE on disease-specific biomarkers levels

3 Study Design and Endpoints

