7.3 Time Period and Frequency for Event Assessment and Follow-Up

The occurrence of an AE or SAE may come to the attention of study personnel during study visits and interviews of a study participant presenting for medical care, or upon review by one of investigators. All AEs including local and systemic reactions not meeting the criteria for SAEs will be captured on the appropriate eCRF. Information to be collected includes event description, time of onset, clinician's assessment of severity, relationship to study procedure (assessed only by those with the training and authority to make a diagnosis), and time of resolution/stabilization of the event. All AEs occurring while on study must be documented appropriately regardless of relationship. All AEs will be followed to adequate resolution.

Any medical condition that is present at the time that the participant is screened will be considered as baseline and not reported as an AE. However, if the study participant's condition deteriorates at any time during the study, it will be recorded as an AE. UPs will be recorded in the data collection system throughout the study.

Changes in the severity of an AE will be documented to allow an assessment of the duration of the event at each level of severity to be performed. AEs characterized as intermittent require documentation of onset and duration of each episode.

The PI will record all reportable events with start dates occurring any time after informed consent is obtained until 7 (for non-serious AEs) or 30 days (for SAEs) after the last day of study participation. At each study visit, the investigator will inquire about the occurrence of AE/SAEs since the last visit. Events will be followed for outcome information until resolution or stabilization.

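### Adverse event rates are planned as simple proportions with no named denominator and no allowance for unequal follow-up, so later events would tend to read low

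*Combined protocol and SAP*

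**What the plan says.** Section 2.2 gives the first secondary objective as "Safety of GAE evaluated by cumulative rates of adverse events (AE), as well as type, causality, and severity of each AE". No time horizon is attached to it, whereas the efficacy items in the same list name months 3, 6, 12 and 24.

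Section 9.4.4 supplies the estimator: "Safety endpoints will assess adverse event rate (defined as the proportion of patients showing each type of adverse event or any adverse event". Section 9.4.3 uses the same definition and adds that "A point estimate and 95% confidence interval will be provided for each secondary outcome at each time". Neither section names a denominator, and neither mentions person-time, censoring or cumulative incidence.

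Four other statements bear on how the proportion would behave:

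- **Length of follow-up.** The Protocol Summary states: "Patients will be followed up for a total of 24 months after GAE".
- **Attrition.** Section 9.5 states that "with 20% attrition, the study will need 50 subjects to reach the target sample size", the target being 40 patients with a 6-month visit. No loss figure is given for months 6 to 24.
- **Recording window.** Under section 7.3, reportable events are recorded from consent "until 7 (for non-serious AEs) or 30 days (for SAEs) after the last day of study participation".
- **Analysis set.** Section 9.3 limits the analysis to patients who received the device and completed at least the 3-month visit. It does not say whether this applies to safety.

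Section 9.1 rules out a separate formal SAP, so the plan points to no later document that would settle these points.

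**The concern.** A proportion of patients with an event estimates cumulative risk only if everyone is observed over the same period. When some leave early, a patient who stays in the denominator but is no longer observed counts as event-free. The figure then falls as loss rises, whatever the true risk.

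For complications of the procedure itself this hardly matters, because they appear before many patients can be lost. It matters for later events. Section 1.4.1 names osteonecrosis among the AEs to be checked at each follow-up visit, and the embolic is non-resorbable.

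There is a second problem. If section 9.3 governs safety, a treated patient who leaves before the 3-month visit drops out altogether. If the reason for leaving was an AE, the analysis loses the kind of patient it most needs to count.

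**Working it through.** **The plan's own figure.** 40 / (1 - 0.20) = 50, which reproduces the enrolment target in section 9.5. The 20% is therefore loss between accrual and the 6-month visit.

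**Assumptions.** The documents give no AE risks and no loss after month 6. I assume true 24-month risks R of 10% and 20%, and total loss F by month 24 of 20%, 30% or 40%. Loss is independent of AEs, and all of it occurs after treatment. Loss hazard is constant within months 0-6 and within months 6-24.

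**Formula.** The expected crude proportion is the integral over 0-24 months of f(t) x G(t), where f is the density of first-event time and G(t) is the probability of still being observed. For a constant AE hazard, h = -ln(1 - R)/24. The loss hazard is -ln(0.8)/6 = 0.0372 per month to month 6, then -ln((1 - F)/0.8)/18.

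**Worked case: R = 10%, F = 20%, all treated patients in the denominator.** h = 0.00439.

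- Months 0-6: 0.00439/(0.00439 + 0.0372) x (1 - 0.7792) = 0.0233
- Months 6-24: 0.8 x (0.9740 - 0.9000) = 0.0592
- Sum: 0.0825, against a true 0.100

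In 50 patients the shortfall is 50 x (0.100 - 0.0825) = 0.9 patient.

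**Same case, section 9.3 set.** The probability of remaining to month 3 is the square root of 0.8, or 0.894. Dividing by it removes earlier losses from the denominator.

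- Months 0-3: 0.0131
- Months 3-6: 0.0122
- Months 6-24: (0.8/0.894) x 0.0740 = 0.0662
- Sum: 0.0915

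**Constant hazard, all cases:**

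| True risk | Lost by month 24 | All treated | Relative shortfall | 9.3 set | Relative shortfall |
|---|---|---|---|---|---|
| 10% | 20% | 8.3% | 17% | 9.2% | 9% |
| 10% | 30% | 7.9% | 21% | 8.7% | 13% |
| 10% | 40% | 7.5% | 25% | 8.3% | 17% |
| 20% | 20% | 16.5% | 17% | 18.3% | 8% |
| 20% | 30% | 15.8% | 21% | 17.5% | 12% |
| 20% | 40% | 15.0% | 25% | 16.7% | 17% |

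**Events only after month 6.** With no later loss, a true 10% reads 0.8 x 10% = 8.0% over all treated patients (20% low). Over the 9.3 set it reads (0.8/0.894) x 10% = 8.9% (11% low). With 40% lost by month 24, the 9.3-set shortfall reaches 22%. If loss ran on at the early rate, 1 - 0.8^4 = 59% would be lost by month 24, and a true 10% over all treated patients would read 5.9%.

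**Events only in the first 10 days.** A true 10% reads 9.9%, a relative shortfall under 1%.

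**Sensitivity to the denominator.** Take 50 treated, 40 observed to month 24 and a 10% late risk, giving 40 x 0.10 = 4 expected events. The rate reads 4/50 = 8.0% if no early loss is removed, 4/45 = 8.9% if half are removed, and 4/40 = 10.0% if all are removed.

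**The case against.** The strongest reply is that this is an ordinary small-pilot safety summary. Section 3.2.2 plans counts and simple statistics for complications, and a proportion with an event so far is a normal meaning of a cumulative rate. Section 6.3.4.1 expects most complications to be evident by the day 7 visit, where the bias is negligible. Section 4.7.2 asks for every effort to capture AEs after withdrawal, and section 7.3 asks for later related events to be notified. Precision is also poor: an exact 95% interval for 5/50 runs from about 3% to 22%, far wider than a shift from 10% to 8.3%.

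Most of that stands, and it keeps the point small. It does not remove it. Capture after withdrawal is best effort with no stated duration and cannot reach patients lost to contact. Wide intervals do not correct a shift in one direction.

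A reader might go further and infer that section 2.2 promises 24-month cumulative rates and that 9.4.4 breaks the promise by treating everyone as observed for 24 months. The documents do not support this. Section 2.2 sets no horizon. Section 9.4.3 plans estimates at each time, without saying whether they are cumulative or who is in the denominator. Nor can the 17-25% be read as a fixed bias, since it needs all treated patients in the denominator. Section 9.3 may remove some early losses. Section 4.4 counts patients who completed both the procedure and the 6-month visit, so some attrition may even precede treatment. If all early losses left the denominator and nobody was lost later, late events would show no bias.

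**Conclusion.** The plan leaves the AE estimator under-specified: a simple proportion, no denominator, no stated safety set and no rule for unequal follow-up. For events spread evenly over 24 months the likely understatement is about 17-25% relative with all treated patients counted, or about 8-17% with the 9.3 set. For events only after month 6, the 9.3-set figure is 11-22%. These ranges rest on the plan's 20% loss by month 6 and on assumed independent loss, 20-40% total loss by month 24 and true risks of 10-20%.

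This is a minor, worthwhile correction. The primary endpoint is untouched and first-week events are reported almost without bias. The possible exclusion of treated patients who leave before month 3 does not depend on these assumptions and should be closed whatever view is taken of the rest.

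**What to change.** In section 9.4.4:

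1. Define the safety set as all patients who received the device, and state that the 3-month-visit condition in section 9.3 does not apply to safety.
2. For any AE, and for key late AE types such as osteonecrosis, report cumulative incidence from Day 0, censored at last contact, with death as a competing event (Aalen-Johansen). Give it at day 7 and months 3, 6, 12 and 24 with 95% confidence intervals and numbers still in follow-up.
3. Keep the crude counts and proportions beside these estimates. For other AE types, where events will be few, counts are enough.
4. List AEs between consent and Day 0 separately, since recording starts at consent.

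No new data are needed. Section 7.3 already provides that "Information to be collected includes event description, time of onset". The cost is a few sentences of text and slightly more analysis, and late AE rates will look slightly less favourable.
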